9.5. Sample Size Determination

The incidence of those participants with a different PK profile (2 of 19 subjects in Study LOXO-RET-18015) has meant that Lilly is planning to enroll up to approximately 60 participants in Stage 1. This is to ensure that at least 50 participants will complete Stage 1 and a sufficient variation of gastric pH will be incorporated in Stage 1.

If the true intraparticipant CV is 30% for C_{max} and 20% for AUC, the first 50 participants in Stage 1 will give approximately 90% power to meet BE criteria at a 1-sided α level of 0.05, under an assumption of a GMR of 1.05.

Table JZJZ.9.1 shows the required sample size for Stage 2 to provide the power for C_{max} of 90% based on different intrasubject CV for C_{max} from Stage 1, assuming the true tablet-to-capsule GMR is 1.05 under scenario when the power is less than 90% and BE is not met at Stage 1. The actual sample size for Stage 2 will be determined based on the observed intrasubject CV at Stage 1.

In Stage 1, dropouts will not be replaced.

In Stage 2, dropouts will not be replaced, but over-enrollment of up to 20% of the determined sample size will be permitted to ensure a sufficient number of participants.

Table JZJZ.9.1. Sample Size for Stage 2 Based on Intrasubject CV for C_{max} in Stage 1

Intrasubject CV for C_{max} in Stage 1	Required Sample Size for Stage 2
40%	50
50%	100
60%	156
70%	216

Abbreviations: C_{max} = maximum serum concentration; CV = coefficient of variation.

Note: The total sample size will be at least 50 for Stage 1 plus the required sample size for Stage 2.

10. Supporting Documentation and Operational Considerations

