9.4. Interim Analysis

At completion of Stage 1, an interim analysis will be conducted to test BE and estimate the power before continuing to Stage 2.

In order to meet the BE criterion at a specific α level, the 2-sided confidence interval for the tablet-to-capsule (tablet formulation / capsule formulation) geometric mean ratio (GMR) for

AUC and C_{max} at the $(1-2\alpha)$ level should fall within 80%-125%. The sequential design approach of Potvin's Method C will be used to preserve the overall type I error rate at the 1-sided significance level of 0.05.

The BE testing and alpha spending scheme is described in [Figure JZJZ.9.1](#). At an interim analysis, the power will be evaluated using the intrasubject CV from Stage 1 using α level of 0.05 assuming the true tablet-to-capsule GMR is 1.05. If Stage 1 has at least 90% power, BE will be tested at Stage 1 at an α level of 0.05. The study will be stopped whether BE is met or not met. The evaluation of the power at Stage 1 will be based on C_{max} , which has higher variability. If the power is less than 90%, BE will be tested at an α level of 0.0294 as originally proposed by Pocock (Pocock 1977). If the BE criterion is met, the study will be stopped. If the BE criterion is not met, the sample size for Stage 2 will be calculated based on the intrasubject CV at Stage 1 and an α level of 0.0294 assuming the true tablet-to-capsule GMR is 1.05, and Stage 2 will be initiated. At Stage 2, BE will be evaluated using data from both stages at an α level of 0.0294.

[figure not shown]

Figure JZJZ.9.1. Adaptive sequential design method C (Potvin, 2007).

The Statistical Analysis Plan will describe the planned interim analyses in greater detail.

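### The Stage 2 sizes are described as giving 90% power for Cmax once Stage 1 has failed BE; in that scenario the CV 40% and 50% rows give about 79% and 87%

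*Protocol*

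**What the plan says.** Protocol 9.5 introduces Table JZJZ.9.1 as the Stage 2 size needed for Cmax power "of 90% based on different intrasubject CV for C_{max} from Stage 1", with a true ratio of 1.05, "under scenario when the power is less than 90% and BE is not met at Stage 1". The rows are 50, 100, 156 and 216 participants for CVs of 40%, 50%, 60% and 70%. The table note adds: "The total sample size will be at least 50 for Stage 1 plus the required sample size for Stage 2". SAP 7 repeats the table and the same scenario wording.

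Protocol 9.4 and SAP 10 set the decision path:

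- "If Stage 1 has at least 90% power, BE will be tested at Stage 1 at an α level of 0.05", and the study then stops.
- "If the power is less than 90%, BE will be tested at an α level of 0.0294". If BE is met, the study stops.
- If BE is not met, Stage 2 follows without further choice. Its size comes from the Stage 1 CV, alpha 0.0294 and an assumed true ratio of 1.05.
- The final test pools the stages: "At Stage 2, BE will be evaluated using data from both stages at an α level of 0.0294".

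The sizing rule does not use the Stage 1 point estimate. Neither document says whether the 90% is unconditional or applies given a failed Stage 1.

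**The concern.** The sentence ties 90% power to one branch of the design, the one in which Stage 1 has already missed BE. Sizing the pooled total as a single fixed-size test ignores that condition. A trial that misses BE at Stage 1 has, on average, a Stage 1 ratio further from 1 than the true ratio, and that estimate stays in the final pooled test. Power in that branch must therefore be lower than the unconditional figure wherever Stage 1 has a fair chance of succeeding, which means at the lower CVs. These are also the rows nearest the planning CV of 30%. At stake is the accuracy of a stated power: a reader would take the chance of failure after Stage 2 to be 10% in every row.

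**Working it through.** **Inputs.** From Protocol 9.4 and 9.5: BE limits 0.80 to 1.25, true ratio 1.05, alpha 0.05 for the Stage 1 power check, alpha 0.0294 for the Stage 1 test in this branch and for the pooled test, 50 participants in Stage 1, and Stage 2 sizes from the table. Assumed: the true CV equals the row CV.

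**Formulas (2×2 crossover, log scale).** Within-participant variance s² = ln(1 + CV²). Standard error of the log ratio with N participants = √(2s²/N). BE is met when estimate ± t(1−α, df) × SE lies within ±ln 1.25 = ±0.2231. Exact power integrates over the distribution of the estimated variance, with df = N − 2.

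**Step 1. Stage 1 statement.** N = 50, CV 30%, alpha 0.05 gives power 0.898. The plan says approximately 90%, so this reproduces.

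**Step 2. The table as unconditional power.** For CV 40%, s² = ln 1.16 = 0.1484 and N = 100, so SE = √(0.2968/100) = 0.0545. The distance from ln 1.05 to the upper limit is 0.2231 − 0.0488 = 0.1743. As a rough check, 0.1743/0.0545 − 1.91 ≈ 1.29, a normal probability of about 0.90. Exact results at alpha 0.0294:

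| CV | Pooled N | Unconditional power | Smallest even N for 90% |
|---|---|---|---|
| 40% | 100 | 0.8988 | 102 |
| 50% | 150 | 0.8999 | 152 |
| 60% | 206 | 0.8999 | 208 |
| 70% | 266 | 0.8993 | 268 |

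The table reproduces within 2 participants per row. Alpha 0.05 would need totals of only 86, 128, 176 and 228, so the table was built on the pooled total at 0.0294, as Protocol 9.4 specifies.

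**Step 3. Power in the stated scenario.** The two-stage procedure was simulated with 2,000,000 trials per row: Stage 1 of 50, Stage 2 from the table, and a pooled test at 0.0294 with df N − 4. The condition was observed Stage 1 power below 90% (observed CV above about 29.9%) and Stage 1 BE not met at 0.0294. The overall column also counts the few trials that pass the power check and are tested at 0.05.

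| CV | Stage 1 alone meets BE at 0.0294 | Reaches Stage 2 | Power given Stage 2 reached | Overall two-stage power |
|---|---|---|---|---|
| 40% | 57% | 43% | 0.79 | 0.91 |
| 50% | 29% | 71% | 0.87 | 0.91 |
| 60% | 9% | 91% | 0.89 | 0.90 |
| 70% | 2% | 98% | 0.90 | 0.90 |

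**Step 4. Consistency at CV 40%.** About 0.573 of trials succeed at Stage 1 (including those tested at 0.05) and 0.426 go on. Then 0.573 + 0.426 × 0.791 = 0.573 + 0.337 = 0.910, the overall figure.

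**Step 5. Why the rows differ.** Among trials that fail Stage 1, the geometric mean of the Stage 1 ratio is about 1.10 at CV 40% and 1.07 at CV 50%, against a true 1.05. At CV 40%, Stage 1 supplies half the pooled data, so the expected pooled log ratio is (ln 1.10 + ln 1.05)/2 = (0.0953 + 0.0488)/2 = 0.072. The distance to the limit shrinks from 0.174 to 0.151. At the higher CVs nearly every trial fails Stage 1, so failing it selects little, and Stage 1 carries less weight.

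**Sensitivity.** Fixing the observed Stage 1 CV at the row value gives 79.2%, 87.1%, 89.7% and 89.9%. With the observed CV fixed in this way, 60 Stage 1 completers leave the first two rows at 79% and 87%.

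**The case against.** The scenario phrase can be read as saying only when the table is used, since it matches the branch in which a Stage 2 size is calculated at all. On that reading nothing is claimed about power given failure, and the sizing rule in Protocol 9.4, which ignores the Stage 1 estimate, fits it. That reading is available and makes this a fault of wording and not of sizing. It does not remove the need for a change: the sentence joins 90% to that scenario without qualification, and neither document gives any other definition.

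It is also fair to say that lower power among trials that go on is expected whenever successes stop early, and that overall power meets the target. Both statements stand.

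The permitted 20% over-enrollment does not close the gap. If every extra participant completed, power given Stage 2 would be about 84% at CV 40% (60 participants) and 91% at CV 50% (120), but the allowance is there to cover dropouts.

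Two stronger readings are tempting, and the documents do not support them. The first is that the table is miscalculated or the study underpowered; the table reproduces and overall power is 90-91%. The second is that the sponsor would decide whether to run Stage 2 from this table; Protocol 9.4 starts Stage 2 automatically once BE is missed in this branch, and Protocol 9.5 sets the actual size from the observed CV. No decision rule depends on conditional power.

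**Conclusion.** The point holds as a correction to a stated property. In the scenario the plan names, the chance of failing BE for Cmax after Stage 2 is about 21% at CV 40% and 13% at CV 50%, where the wording implies 10%. The 60% and 70% rows are right to within about a percentage point.

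These figures are for Cmax alone, as in the table, and assume 50 Stage 1 completers, the tabulated Stage 2 size, a true ratio of 1.05 and a true CV equal to the row value. For information, 90% power in the stated scenario would take roughly 75 Stage 2 participants instead of 50 at CV 40%, and about 114 instead of 100 at CV 50%. The documents do not commit to that target as a design requirement, and overall power does not need it.

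**What to change.** Keep the sizes, alpha levels and decision rules. In Protocol 9.5 and SAP 7, replace the description of the table with wording such as:

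> These sizes give about 90% unconditional power for the pooled Cmax analysis at alpha 0.0294 (overall two-stage power about 90-91%). Assuming 50 Stage 1 completers, the Stage 2 size shown, a true GMR of 1.05 and a true CV equal to the row value, the probability of meeting BE for Cmax after Stage 2, given that Stage 1 power was below 90% and BE was not met, is about 79%, 87%, 89% and 90% for CVs of 40%, 50%, 60% and 70%.

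The cost is a text change in two documents and a less favourable stated figure in two rows. No participants are added.

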10.1. Appendix 1: Regulatory, Ethical, and Study Oversight Considerations

10.1.1. Regulatory and Ethical Considerations

- This study will be conducted in accordance with the protocol and with the following:
 - Consensus ethical principles derived from international guidelines including the Declaration of Helsinki and Council for International Organizations of Medical Sciences International Ethical Guidelines
 - Applicable ICH Good Clinical Practice (GCP) Guidelines
 - Applicable laws and regulations
- The protocol, protocol amendments, ICF, Investigator Brochure, and other relevant documents (for example, advertisements) must be submitted to an IRB/IEC by the investigator and reviewed and approved by the IRB/IEC before the study is initiated.
- Any amendments to the protocol will require IRB/IEC approval before implementation of changes made to the study design, except for changes necessary to eliminate an immediate hazard to study participants.
- Protocols and any substantial amendments to the protocol will require health authority approval prior to initiation except for changes necessary to eliminate an immediate hazard to study participants.
- The investigator will be responsible for the following:
 - Providing written summaries of the status of the study to the IRB/IEC annually or more frequently in accordance with the requirements, policies, and procedures established by the IRB/IEC
 - Notifying the IRB/IEC of SAEs or other significant safety findings as required by IRB/IEC procedures
 - Providing oversight of study conduct for participants under their responsibility and adherence to requirements of 21 Code of Federal Regulations (CFR), ICH guidelines, the IRB/IEC, European regulation 536/2014 for clinical studies (if applicable), and all other applicable local regulations
- Investigator sites are compensated for participation in the study as detailed in the Clinical Trial Agreement.

10.1.2. Informed Consent Process

- The investigator or his/her representative will explain the nature of the study, including the risks and benefits, to the participant and answer all questions regarding the study.

- Participants must be informed that their participation is voluntary. Participants will be required to sign a statement of informed consent that meets the requirements of 21 CFR 50, local regulations, ICH guidelines, privacy and data protection requirements, where applicable, and the IRB/IEC or study center.
- The medical record must include a statement that written informed consent was obtained before the participant was entered in the study and the date the written consent was obtained. The authorized person obtaining the informed consent must also sign the ICF.
- Participants must be reconsented to the most current version of the ICF(s) during their participation in the study.
- A copy of the ICF(s) must be provided to the participant and is kept on file.

10.1.3. Data Protection

- Participants will be assigned a unique identifier by the sponsor. Any participant records, datasets or tissue samples that are transferred to the sponsor will contain the identifier only; participant names or any information which would make the participant identifiable will not be transferred.
- The participant must be informed that his/her personal study-related data will be used by the sponsor in accordance with local data protection law. The level of disclosure must also be explained to the participant who will be required to give consent for his/her data to be used as described in the informed consent.
- The participant must be informed that his/her medical records may be examined by Clinical Quality Assurance auditors or other authorized personnel appointed by the sponsor, by appropriate IRB/IEC members, and by inspectors from regulatory authorities.
- The sponsor has processes in place to ensure data protection, information security and data integrity. These processes include appropriate contingency plan(s) for appropriate and timely response in the event of a data security breach.

10.1.4. Dissemination of Clinical Study Data

Communication of Suspended or Terminated Dosing

If a decision is taken to suspend or terminate dosing in the trial due to safety findings, this decision will be communicated by Lilly to all investigators (for example, by phone and/or email) as soon as possible. It will be a requirement that investigators respond upon receipt to confirm that they understand the communication and have taken the appropriate action prior to further dosing any participants with study intervention. Any investigator not responding will be followed up by Lilly personnel prior to any further planned dosing. If a dose is planned imminently, Lilly personnel will immediately, and continually, use all efforts to reach investigators until contact is made and instructions verified.

Reports

The sponsor will disclose a summary of study information, including tabular study results, on publicly available websites where required by local law or regulation.

Data

The sponsor does not proactively share data from Phase 1 clinical trials. Requests for access to Phase 1 clinical trial data are evaluated on a case-by-case basis taking into consideration the ability to anonymize the data and the nature of the data collected.

10.1.5. Data Quality Assurance

- All participant data relating to the study will be recorded on printed or electronic case report forms (CRFs) unless transmitted to the sponsor or designee electronically (for example, laboratory data). The investigator is responsible for verifying that data entries are accurate and correct by physically or electronically signing the CRF.
- The investigator must maintain accurate documentation (source data) that supports the information entered in the CRF.
- The investigator must permit study-related monitoring, audits, IRB/IEC review, and regulatory agency inspections and provide direct access to source data documents.
- Quality tolerance limits (QTLs) will be predefined to identify systematic issues that can impact participant safety and/or reliability of study results. These pre-defined parameters will be monitored during the study and important excursions from the QTLs and remedial actions taken will be summarized in the clinical study report.
- Monitoring details describing strategy (for example, risk-based initiatives in operations and quality such as risk management and mitigation strategies and analytical risk-based monitoring), methods, responsibilities and requirements, including handling of noncompliance issues and monitoring techniques are provided in the Monitoring Plan.
- The sponsor or designee is responsible for the data management of this study including quality checking of the data.
- The sponsor assumes accountability for actions delegated to other individuals (e.g., contract research organizations).
- Study monitors will perform ongoing source data verification to confirm that data entered into the CRF by authorized site personnel are accurate, complete, and verifiable from source documents; that the safety and rights of participants are being protected; and that the study is being conducted in accordance with the currently approved protocol and any other study agreements, ICH GCP, and all applicable regulatory requirements.

- Records and documents, including signed ICFs, pertaining to the conduct of this study must be retained by the investigator for the time period outlined in the Clinical Trial Agreement unless local regulations or institutional policies require a longer retention period. No records may be destroyed during the retention period without the written approval of the sponsor. No records may be transferred to another location or party without written notification to the sponsor.
- In addition, sponsor or its representatives will periodically check a sample of the participant data recorded against source documents at the study site. The study may be audited by sponsor or its representatives, and/or regulatory agencies at any time. Investigators will be given notice before an audit occurs.

Data Capture System

The investigator is responsible for ensuring the accuracy, completeness, legibility, and timeliness of the data reported to the sponsor.

Data collected via the sponsor-provided data capture system will be stored at third-party. The investigator will have continuous access to the data during the study and until decommissioning of the data capture system. Prior to decommissioning, the investigator will receive an archival copy of pertinent data for retention.

Data managed by a central vendor, such as laboratory test data, will be stored electronically in the central vendor's database system and electronic transfers will be provided to the investigator for review and retention. Data will subsequently be transferred from the central vendor to the sponsor data warehouse.

Data from complaint forms submitted to sponsor will be encoded and stored in the global product complaint management system.

10.1.6. Source Documents

- Source documents provide evidence for the existence of the participant and substantiate the integrity of the data collected. Source documents are filed at the investigator's site.
- Data reported on the CRF or entered in the eCRF that are transcribed from source documents must be consistent with the source documents or the discrepancies must be explained. The investigator may need to request previous medical records or transfer records, depending on the study. Also, current medical records must be available.
- Definition of what constitutes source data can be found in [10.1.5](#).

10.1.7. Study and Site Start and Closure

First Act of Recruitment

The study start date is the date on which the clinical study will be open for recruitment of participants.

Study or Site Termination

The sponsor designee reserves the right to close the study site or terminate the study at any time for any reason at the sole discretion of the sponsor. Study sites will be closed upon study completion. A study site is considered closed when all required documents and study supplies have been collected and a study site closure visit has been performed.

The investigator may initiate study site closure at any time, provided there is reasonable cause and sufficient notice is given in advance of the intended termination.

Reasons for the early closure of a study site by the sponsor or investigator may include but are not limited to:

For study termination:

- Discontinuation of further study intervention development

For site termination:

- Failure of the investigator to comply with the protocol, the requirements of the IRB/IEC or local health authorities, the sponsor's procedures, or GCP guidelines
- Inadequate recruitment (evaluated after a reasonable amount of time) of participants by the investigator
- Total number of participants included earlier than expected.

If the study is prematurely terminated or suspended, the sponsor shall promptly inform the investigators, the IECs/IRBs, the regulatory authorities, and any contract research organization(s) used in the study of the reason for termination or suspension, as specified by the applicable regulatory requirements. The investigator shall promptly inform the participant and should assure appropriate participant therapy and/or follow-up.

10.1.8. Publication Policy

In accordance with the sponsor's publication policy, the results of this study will be submitted for publication by a peer-reviewed journal if the results are deemed to be of significant medical importance.

10.2. Appendix 2: Clinical Laboratory Tests

The tests detailed in the table below will be performed by the local laboratory.

Protocol-specific requirements for inclusion or exclusion of participants are detailed in Section 5 of the protocol.

Additional tests may be performed at any time during the study as determined necessary by the investigator or required by local regulations.

Investigators must document their review of the laboratory safety results.

Safety Laboratory Tests

Hematology	Clinical Chemistry
Hematocrit	Sodium
Hemoglobin	Potassium
Erythrocyte count (RBC)	Bicarbonate (total CO ₂)
Mean cell volume	Chloride
Mean cell hemoglobin	Calcium
Mean cell hemoglobin concentration	Phosphorus
Leukocytes (WBC)	Glucose (random)
Platelets	Creatine kinase
	Total cholesterol, LDL-C, and HDL-C
Differential WBC (absolute counts) of	
Neutrophils	Blood urea nitrogen (BUN)
Lymphocytes	Uric acid
Monocytes	Gamma-glutamyl transferase (GGT)
Eosinophils	Total protein
Basophils	Albumin
Urinalysis	
Specific gravity	Total bilirubin
pH	Alkaline phosphatase (ALP)
Protein	Aspartate aminotransferase (AST)
Glucose	Alanine aminotransferase (ALT)
Ketones	Creatinine
Bilirubin	Ethanol testing ^b
Urobilinogen	Urine drug screen ^b
Blood	Hepatitis B surface antigen ^c
Nitrite	Hepatitis C antibody ^{c, d}
Leukocyte esterase	HIV ^c
	Pregnancy test (women of childbearing potential only)
	FSH (if applicable) ^{c, e}

Abbreviations: FSH = follicle-stimulating hormone; HIV = human immunodeficiency virus; RBC = red blood cell; WBC = white blood cell.

- a Performed by dipstick. Microscopic examination to be performed if dipstick is abnormal for blood, protein, nitrites, or leukocyte esterase.
- b Urine drug screen and ethanol (urine) level performed at screening and check-in.
- c Performed at screening only.
- d Participants with a positive hepatitis C antibody test result can have a confirmatory hepatitis C RNA test.
- e Postmenopausal women only.

